## SCHEMA

\*N=60-80 includes participants from Arm C who have services via the waitlist.

\*\*6-Month Outcome Survey also given to participants on Arms A and B that have lost contact with Penn Telegenetics before receiving genetic services

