##### 1. Randomization

Upon successful completion of informed consent and baseline (T0) survey, participants will be randomized into one of three potential study arms. Randomization assignments will be determined by a permuted block design and stratified by male/female/other. Study arms will consist of variations of methods of delivery for genetic counseling.

Once enrollment goals for Aim 1 are reached (120 completed baseline survey and sent randomization flyer), we will halt enrollment of Arm C. We will continue to enroll to Arms A and B to meet enrollment goals for Aim 2.

ARM	COUNSELING METHOD
ARM A	Remote Videoconference Telegenetics
ARM B	Remote Phone Telegenetics
ARM C	Usual Care

After randomization, participants will be sent information flyers (**Appendix E**) via the myLTU app that correspond to the appropriate arm to which they have been randomized. Flyers will include instructions for how to contact the Penn Telegenetics team to schedule their appointment (Arms A and B) or usual care options (Arm C) for obtaining genetic services (e.g. ask PCP or providers, use the National Society of Genetic Counselors website [www.nsgc.org](http://www.nsgc.org)).

Participants will be followed up with by a member of the research team to ensure they have received the flyers with the randomization assignment and information. Participants in all arms will be fully informed of how to initiate genetic services, and that it is their responsibility to do so.

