## OUTCOMES AND MEASURES

Table 1. Effectiveness outcomes and measures			
CONSTRUCT	T0	T1	T2-T4
Moderators of patient outcomes			
Sociodemographics	X		
Cancer history	X		
Family history	X		
Health literacy	X		
Comfort with technology	X		
Self-efficacy	X		
Financial Wellness	X		
COVID Impact	X		X
Outcomes			
Uptake counseling, testing, identification carriers at 6 months* (Telegenetics records for Arms A/B & the 6-Month Status Survey in Arm C)			
Understanding of Genetic Information**			
Test result recall			X
Knowledge of genetic disease	X	X	X
Perceived risk	X	X	X
Reactions to genetic information**			
Anxiety and Depression	X	X	X
Cancer specific distress	X	X	X
Satisfaction with genetic services and telemedicine		X	X
Behavioral use of genetic information**			
Performance of behaviors	X		X
Cost (patient and system)**		X	X

\*Aim 1; \*\*Aim 2; T0=baseline (within 30 days of visit 1, can accept within 45 days. beyond that it needs to be updated), waitlist usual care participants will need to complete a new baseline, T0b; T1=survey post pre-test counseling, Visit 1 (ideally collect 1-3 days and up to 7 days. accept up to 14 days but from 7-14 days we may elect to drop and impute). T2=survey immediately post genetic testing disclosure (same timing as T1); T3/T4 survey=6/12-month post genetic testing disclosure (ideally get within 14 days of 6/12 month mark but accept within 60 days of 6 month or 12 month mark)

The T0-T4 patient surveys for the RCT will be completed through a secure website, linked through the myLTFU platform. The 6-Month Outcome Survey will be administered by phone. If the phone survey cannot be completed, the survey will be offered self-administered through the myLTFU platform.

Effectiveness Outcomes (Aims 1 and 2):

**1) Uptake of counseling, testing and identification of carriers at 6 months** (Aim 1): This information will be obtained through study records for Arms A and B (intervention arms) and the 6-Month Outcome Survey among nonresponders in Arm A and B (e.g. those who did not contact Penn Telegenetics or did not complete visit 1 or visit 2) and in Arm C (usual care). The outcome survey will query completion of each outcome, date, and provider and will explore barriers and reasons for no uptake (Appendix I).

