comparisons between the remote videoconferencing versus phone groups, we will assign participants to the remote group assigned at baseline, or after rerandomization for the waitlist group. Our primary change scores for the first three variables will be change between baseline and immediately post genetic testing. For the waitlist group, there will be a second baseline measurement after the usual care period has ended. For the 3 primary analyses in Aim 2, we will use T-tests. We will assess balance of potential confounders (e.g. age, race, study site, waitlist assignment) between arms using T-tests or Fisher's exact tests as appropriate. Waitlist group will be considered a confounder in these secondary regression analyses. We will use multiple linear regression models to control for potential confounders inadequately balanced. We will include in the models the confounding variables and indicator (binary 0/1 variables) to indicate randomization arms (leaving one group out as the reference). For longitudinal analyses, we will examine time trajectories using regressions estimated by Generalized Estimating Equations (GEE) to account for within subject temporal correlation. Panel time will be included via indicator variables. We will also include interaction terms between randomization arm and time indicators to investigate temporal effects.(82) We will repeat analyses, but assign participants to per-protocol (i.e. restricting sample to those who properly used the assigned method of disclosure) or as-treated groups (e.g. assigning all participants to a group based on the method of disclosure used, regardless of assignment). For Aim 2 secondary outcomes, we will use multiple linear regressions for continuous outcomes and multiple logistic regressions for binary outcomes using GEE-estimation as described.

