**Sample Size Justification for Aim 2:** We further chose our sample size such that we would have sufficient power for Aim 2 comparisons of the videoconference versus phone arms. After rerandomization of the waitlist group, we anticipate potentially having 180 people/arm randomized to the videoconference or phone arms. Based on prior experience, we anticipate that loss to follow-up will be less than 28% in each arm, leaving us with 130 evaluable participants with follow-up data in each group ( $180 - 180 \times 0.28 = \text{approximately } 130$ ). Some of the loss to follow-up will occur prior to the waitlist group being rerandomized. We used our pilot data to determine power for this aim (see Table 2 for estimates). We assumed 85% power and a 1.67% Type I error rate. We used a 1.67% Type 1 error rate (2-sided) by applying a Bonferroni correction for the three outcomes of interest to the typical 5% Type I error rate ( $5\% / 3 = 1.67\%$ ). We see in Table 2 that we have excellent power for all three arms with at least 95/arm, which is well below our expected 130/arm anticipated sample size. Table 2 also demonstrates that we have sufficient power for subgroup analyses, with a sample size of just 22/arm needed for knowledge comparisons between arms.

Table 2. Sample size calculations for Aim 2		
Variable	Change scores + (SD) of phone vs. videoconferencing	Number needed*
Knowledge	+5.7 (11.2) vs. +18.6 (12.6)	22/arm
Cancer specific distress**	+3.6 (12.4) v. -2.6 (12.3)	95/arm
Depression	-0.2 (2.0) vs. -1.6 (2.0)	50/arm

+Baseline to post genetic testing \*85% Power, 1.67% alpha; \*\*intrusive subscale

Amendment note added June 5, 2023: Our anticipated visit 2 completion sample size for the phone and videoconferencing arms will be 60 to 80 per arm, which is below are initial goal of 180/arm. With 60 to 80 per arm, we will still have adequate power for the knowledge and depression endpoints.

Analyses for Aim 3 included in **Appendix K**.

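### Aim 2a compares video and phone with unadjusted t-tests on change scores; a pre-specified ANCOVA could reduce the distress power shortfall at 60 to 80 per arm without adding patients

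*Combined protocol and SAP*

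**What the plan says.** Section 4.0, Analyses for Aim 2, names three primary outcomes for the video versus phone comparison: cancer-related distress, depression and knowledge. The outcome form is a change score: "Our primary change scores for the first three variables will be change between baseline and immediately post genetic testing". The test is given as "For the 3 primary analyses in Aim 2, we will use T-tests".

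Adjustment comes in only afterwards. Regression models are planned for confounders that turn out poorly balanced, and "Waitlist group will be considered a confounder in these secondary regression analyses". The baseline score and the sex/gender stratum are not named as covariates, although section 3.3 (1. Randomization) says "Randomization assignments will be determined by a permuted block design and stratified by male/female/other".

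Table 2 gives 22, 95 and 50 per arm for knowledge, distress and depression. The note of June 2023 below it says "Our anticipated visit 2 completion sample size for the phone and videoconferencing arms will be 60 to 80 per arm" and continues "With 60 to 80 per arm, we will still have adequate power for the knowledge and depression endpoints". Distress is not mentioned. The Schema adds that "N=60-80 includes participants from Arm C who have services via the waitlist". Under the Table 1 footnote, "waitlist usual care participants will need to complete a new baseline, T0b".

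**The concern.** The expected sample is now below the plan's own requirement for distress, and the plan neither gives the resulting power nor offers a remedy. The primary test also leaves unused information that the trial already collects. A change score subtracts the whole baseline value, whereas ANCOVA estimates how much of it to subtract. With two arms of about equal size, ANCOVA is at least as precise in large samples.

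Two design features also sit outside the primary model: the factor used to stratify randomisation, and whether a participant entered directly or through the Arm C waitlist with a separate baseline.

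The stakes are limited. Video versus phone is a secondary objective (section 4.0, Sample Size Justification for Aim 1), and only one of its three outcomes is short of power. For that outcome, a real effect of the size assumed in Table 2 could be missed more often than planned.

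**Working it through.** **Inputs from the documents** (section 4.0, Sample Size Justification for Aim 2, and Table 2)
- Distress change, phone versus video: +3.6 (SD 12.4) versus -2.6 (SD 12.3)
- Depression change: -0.2 (2.0) versus -1.6 (2.0)
- Knowledge change: +5.7 (11.2) versus +18.6 (12.6)
- Two-sided alpha 5%/3 = 1.67%; target power 85%
- Expected visit 2 completers: 60 to 80 per arm

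**Inputs not in the documents (assumed, shown as ranges)**
- r, the correlation between the baseline and post-disclosure distress scores
- k, the SD after disclosure divided by the SD at baseline

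**Step 1: reproduce Table 2.** The pooled SD for distress is √((12.4² + 12.3²)/2) = 12.35, so d = 6.2/12.35 = 0.502. For depression d = 1.4/2.0 = 0.70. For knowledge d = 12.9/11.92 = 1.08. The noncentral t calculation gives 95, 50 and 22 per arm, exactly as in Table 2.

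**Step 2: power of the planned t-test at the amended size**

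| Outcome | 60 per arm | 80 per arm |
|---|---|---|
| Distress | 62.6% | 77.4% |
| Depression | 91.8% | 97.7% |
| Knowledge | >99% | >99% |

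Distress falls short of the target by 85 - 62.6 = 22.4 points at 60 per arm and by 85 - 77.4 = 7.6 points at 80.

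**Step 3: precision of ANCOVA relative to the change score.** The variance ratio is

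v = (1 - r²)k² / (1 + k² - 2rk).

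The condition v ≤ 1 rearranges to (1 - rk)² ≥ 0, which always holds, with equality only when rk = 1. The effect size becomes d/√v. For example, with k = 1 and r = 0.5, v = 0.75 × 1/(2 - 1) = 0.75 and d/√v = 0.502/0.866 = 0.580.

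**Step 4: distress power with baseline adjustment**

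| k | r | v | 60 per arm | 80 per arm | n per arm for 85% |
|---|---|---|---|---|---|
| 1 | 0.3 | 0.65 | 83.5% | 93.4% | 63 |
| 1 | 0.5 | 0.75 | 77.1% | 89.2% | 72 |
| 1 | 0.7 | 0.85 | 71.0% | 84.6% | 81 |
| 1 | 0.8 | 0.90 | 68.1% | 82.2% | 86 |
| 1.2 | 0.7 | 0.966 | 64.4% | 79.0% | 92 |
| 1.2 | 0.8 | 0.997 | 62.8% | 77.5% | 95 |
| 0.8 | 0.3 | 0.502 | 92.5% | 98.0% | 49 |
| 0.8 | 0.7 | 0.628 | 85.0% | 94.3% | 61 |

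With k = 1, 85% power is reached at 60 per arm only if r is about 0.25 or less, and at 80 per arm only if r is about 0.68 or less.

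**Step 5: simulate the full model.** Step 4 is a large-sample result for the baseline term alone. A simulation (6,000 trials per cell) fitted baseline, a two-level sex covariate and a waitlist indicator. The last two were given assumed prevalences of 50% and 33% and no prognostic value.

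| k, r | t-test, 60 / 80 per arm | ANCOVA, 60 / 80 per arm |
|---|---|---|
| 1, 0.5 | 63.2% / 78.0% | 75.7% / 88.4% |
| 1, 0.8 | 63.3% / 77.8% | 66.1% / 81.4% |
| 1.2, 0.8 | 62.7% / 77.3% | 61.7% / 76.6% |
| 0.8, 0.7 | 62.3% / 76.2% | 84.6% / 93.4% |

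The simulated ANCOVA power is 0.4 to 2.0 points below Step 4 in every cell. In the least favourable cell the full model loses about 1 point against the t-test.

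**The case against.** The t-test is valid and matches Table 2, which is built on change scores, so replacing it improves the plan but does not correct an error. That is right, and the point is put as an improvement.

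A reader can already see the distress shortfall by comparing 95 with 60 to 80. That is also true, but the plan does not give the resulting power.

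The large-sample figures slightly flatter the full model. This stands. Allowing for the finite-sample cost of the covariates, the k = 1 thresholds for 85% power move to about r = 0.21 to 0.22 at 60 per arm and 0.64 to 0.65 at 80. The claimed gain comes from the baseline score only. The sex/gender and waitlist terms are there to reflect the design, and because waitlist participants are themselves re-randomised, waitlist origin should not systematically confound video versus phone.

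The benefit depends on r and k, which are unknown, and it disappears as rk approaches 1. This stands too and limits what can be promised.

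The analysed set is visit 2 completers, a group formed after randomisation. If completion depends on both arm and baseline, ANCOVA and the change score can differ in expectation as well as in precision. ANCOVA does not remove that selection, but the t-test is exposed to it as well.

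Finally, secondary regressions are already planned. They depend on observed imbalance and do not name the baseline score, so they do not raise the power of the primary test.

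**Conclusion.** The concern holds, as an improvement the plan should make. At the expected 60 to 80 per arm, the planned distress test has 62.6% to 77.4% power for the Table 2 effect against a target of 85%, and the plan leaves this unaddressed. Pre-specified baseline adjustment could reduce the gap. The gain ranges from nothing (a loss of about 1 point in the worst simulated case) to about 22 points at 60 per arm in the best simulated case (62.3% to 84.6%). At 60 per arm, most of the range examined still falls short of 85%.

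These figures assume that the Table 2 effect and SDs hold, that arms are about equal, and that all visit 2 completers return the post-disclosure survey; fewer returns would mean less power. The size of the gain rests on assumed r and k. The Aim 1 conclusion, and power for knowledge and depression, are not in question.

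**What to change.** For each of the three Aim 2a outcomes, make the primary analysis an ANCOVA of the T2 score on:
- arm (video versus phone)
- the baseline value of the same scale (T0, or T0b for waitlist participants)
- the sex/gender stratum
- an indicator for waitlist re-randomisation

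Fix these covariates in advance, whatever the balance tests show, and keep the unadjusted change-score t-test as a sensitivity analysis. Say how a sparse third sex/gender category will be handled, and whether the re-randomisation is stratified, which the documents do not state.

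Make the change by a dated amendment before any Aim 2 outcome is compared by arm. In it, state the expected distress power at 60 to 80 per arm over a range of r and k; both can be estimated from T0 and T2 data pooled over arms.

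The cost is the amendment and a few degrees of freedom. All the variables are already collected, so no patients, visits or measurements are added.

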#### 4. Genetic Testing Result Disclosure, Visit 2 (Remote Telegenetics Arms)

**ARM A: Remote telegenetic counseling by videoconference:** The Penn GC will share results with the patient by videoconference at a scheduled visit. The Penn GC will provide the patient's provider with a chart note, summarizing the results and associated implications and cancer risk estimates, as well as standard risk reducing or screening strategies and implications for relatives. Penn GCs will be available to answer PCP/provider questions (by email or phone) and facilitate referral to regional clinical expertise centers as indicated. Patients will be recommended to follow-up with their PCP/provider to implement any screening and medical (including risk reduction) recommendations. If the participant consents, this session will be recorded for research and training purposes.

**ARM B: Remote telegenetic counseling by phone:** The Penn GC will share results with the patient by phone at a scheduled visit. The remainder of procedures for post-test counseling are as described above for Arm A. If the participant consents, this session will be recorded for research and training purposes.

Following the completion of the disclosure session, participants on Arms A and B will also be asked to complete a study survey (T2) (**Appendix H**).

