## 4.0 Statistical Considerations and Analyses

**Analyses for Aim 1:** *We hypothesize that patients randomized to remote telegenetic services will have significantly higher uptake of the composite variable denoting genetic testing or genetic counseling at 6 months.* Our primary outcome will be a composite variable of whether the person had genetic testing or genetic counseling by 6 months (1 if either is true, 0 if neither is true). Uptake of separate genetic testing or genetic counseling decisions (as some patients will make informed decisions to defer testing) and identification of genetic carriers will be three secondary outcomes. We will use Fisher's Exact tests to compare uptake of our primary composite variable and secondary outcomes between the arms. The primary comparison groups will be the usual care/waitlist group vs. the combined remote telegenetics groups (phone

plus videoconference) prior to rerandomization of the waitlist group. For the primary analyses, we will use an intention to treat approach whereby comparisons are made between randomization arms. In secondary analyses, we will compare the randomization arms to investigate if potential confounders (e.g. age) are balanced among the randomization arms. We will do this via pairwise Wilcoxon-rank sum tests and Chi-squared tests as appropriate. If any potential confounders are not found to be balanced among the randomization arms (i.e.  $p < 0.10$  for any potential confounders in pairwise comparisons), we will use multiple logistic regressions of uptake to investigate the randomization arm effect. In these models, we will include randomization arms as binary (0/1) indicator covariates (leaving one out as the reference); we will also include the potential confounders as covariates in the regressions. These regression models will be akin to sensitivity analyses, designed to study if our inferences are robust after accounting for potential confounders.

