To evaluate moderators of patient cognitive, affective and behavioral outcomes (Aim 2b), we will use logistic regressions in which we include variables of interest as covariates. For moderation (i.e. effect modifier analyses), we will include indicator variables for randomization arms in the GEE-estimated multiple linear (for continuous outcomes) or logistic regressions (for uptake); we will also include panel time indicators, the potential moderator variables, and all two-way and three-way interactions among the arm/time/moderator variables. Interactions are created by multiplying two variables together.(82) To maintain power, we will examine non-time moderators separately. We will also examine multiple regression models with potential confounding variables. We will repeat the analyses but assign participants to per-protocol (i.e. restricting sample to those who properly used the method of disclosure as assigned) or as-treated groups (e.g. assigning all participants to a group based on the method of disclosure used, regardless of group assignment).

The economic impact of remote telegenetic services (Aim 2c) will be assessed by performing: 1) cost analysis and 2) cost-effectiveness analysis. The goal of the cost analysis is to estimate the cost of delivering remote telegenetic services, by phone and videoconference, compared to usual care. As above, the cost analysis will take a societal perspective, including the costs of all resources consumed for the implementation and delivery of remote genetic services.

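### The Aim 2b per-protocol and as-treated repeats group people by method of result disclosure, which for the uptake outcome selects on a consequence of uptake

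*Combined protocol and SAP*

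**What the plan says.** In Section 4.0 (Analyses for Aim 2), the Aim 2b paragraph specifies moderator models with randomisation-arm indicators, described as "GEE-estimated multiple linear (for continuous outcomes) or logistic regressions (for uptake"). Uptake is thus named as one of the modelled outcomes. The paragraph ends with two repeats. The per-protocol repeat is introduced by "We will repeat the analyses but assign participants to per-protocol (i.e. restricting sample to those who properly used the method of disclosure as assigned"), and the as-treated repeat is defined by "assigning all participants to a group based on the method of disclosure used, regardless of group assignment". Neither definition is limited to particular outcomes.

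The Aim 1 part of Section 4.0 defines the primary outcome as "a composite variable of whether the person had genetic testing or genetic counseling by 6 months", with counselling and testing also taken separately as secondary outcomes.

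Section 3.3, item 4, describes disclosure as Visit 2. For Arm A, "The Penn GC will share results with the patient by videoconference at a scheduled visit"; for Arm B, "The Penn GC will share results with the patient by phone at a scheduled visit". Items 2 and 3 of the same section leave Arm C to whatever usual-care route each person chooses, so Arm C has no assigned disclosure method until the waitlist re-randomisation.

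**The concern.** A per-protocol or as-treated grouping is meant to describe how the treatment was received, separately from what happened afterwards. Here the grouping variable exists only once the person has been counselled and tested. For knowledge, distress or satisfaction measured after a session this is tolerable, because those outcomes are seen only in people who had the session. For uptake it is not: belonging to a group already implies the outcome.

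An analyst who follows the text has two choices. One is to fit a model that cannot be estimated, or whose estimate does not concern uptake. The other is to depart from the plan without a pre-specified rule. In the near-constant case, a fitted odds ratio close to 1 could be reported as evidence that uptake does not vary by mode or by moderator.

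**Working it through.** **1. The plan's own uptake figure.** The plan gives no figure for the Aim 2b repeats. Its only uptake calculation is for Aim 1: 29/55 = 52.7% versus 4/24 = 16.7%, 240 versus 120 participants, Fisher's exact test, two-sided 1%, with power above 99%. Exact enumeration gives 0.999996, so the figure reproduces. It concerns the randomised comparison, which this point does not touch.

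**2. Order of events in Arms A and B.** Pre-test counselling (Visit 1) comes first, then testing, then disclosure (Visit 2). A disclosure therefore implies testing and counselling. The converse fails: people who stop after Visit 1, people tested elsewhere and people who never make contact have no study disclosure. The per-protocol set keeps only the first kind of participant.

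**3. What the restriction does to uptake.** Assume 120 per telegenetics arm, that uptake means testing, that everyone tested has a disclosure within 6 months by the assigned method, and that no waitlist members are included. The uptake rates below are assumptions chosen to show a true difference between modes.

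| Assumed uptake, video vs phone | All randomised | Odds ratio | Per-protocol set |
|---|---|---|---|
| 60% vs 46% | 72/120 vs 55/120 | (72/48)/(55/65) = 1.77 | 72/72 vs 55/55 |
| 70% vs 36% | 84/120 vs 43/120 | (84/36)/(43/77) = 4.18 | 84/84 vs 43/43 |

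Fisher's p is 1.0 in both restricted tables. An arm-by-moderator logistic model fitted to one simulated data set of 240 people converged on the full sample. On the restricted sample it failed with a singular matrix, because the outcome was constant.

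**4. Allowing for zeros.** Uptake is counted by 6 months, but disclosure has no such limit. Let L be the share of disclosed people in an arm whose 6-month uptake is 0. Restricted uptake is then 1 − L: 95%, 90% or 80% for L = 5%, 10% or 20%. The restricted odds ratio is

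[(1 − L_A)/L_A] / [(1 − L_B)/L_B],

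which does not contain the proportion of each arm that took up services. If L is the same in both arms the ratio is 1, whether the ratio in all randomised people was 1.77 or 4.18. If L is 10% in video and 20% in phone, it is (0.90/0.10)/(0.80/0.20) = 9/4 = 2.25, whatever the uptake rates. The model would be estimating lateness and route of entry.

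**5. Where the zeros come from.** There are two sources: people first served after 6 months, and re-randomised waitlist members. Section 3.3, item 5, offers telegenetic services to Arm C members without testing at 6 months. Their 6-month testing value is therefore 0, and their composite is 0 unless they had counselling only. Neither source carries information on mode or moderator effects on uptake.

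**6. Usual care.** Arm C as originally randomised has no assigned method, so it cannot meet the per-protocol definition. The as-treated wording refers to all participants but gives no rule for people without a disclosure. If they were put in a separate no-disclosure group, that group would be defined almost entirely by the outcome.

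**The case against.** The strongest reply is that the repeats were never meant for uptake. The Aim 2b paragraph opens with patient responses rather than uptake, Table 1 assigns uptake to Aim 1, and the sentence nearly duplicates one in the Aim 2a paragraph, where it does no harm. That may well be the intent, and it is a reason to treat this as a drafting slip. But uptake is named in the same paragraph before the repeat, and nothing excludes it.

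A second reply is that disclosure may loosely mean any session. If it meant Visit 1, testing could vary among those classified, but the composite would still be 1 for everyone served within 6 months.

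A third reply is that a constant outcome fails visibly and so misleads nobody. That is fair for the strictly constant case. It does not cover the near-constant case in step 4, where the model may fit.

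Stronger readings are tempting, and the documents do not support them:

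- A reader might infer that uptake is 100% in every group and that no estimate can exist. The Schema footnote says its N of 60–80 includes Arm C waitlist participants, and some of those who complete Visit 2 will have a 6-month value of 0.
- A reader might infer that usual care is lost altogether. That is firm for the per-protocol set only before re-randomisation. For the as-treated set it is an inference from a missing rule. Aim 2b also concerns outcomes with remote services; the usual-care contrast in uptake belongs to Aim 1.
- A reader might divide the 60–80 Visit 2 completers per arm by an arm size to obtain one excluded share. The numerator may include waitlist entrants, and the denominator is not settled. With 120 per arm the share is 33–50%; with 180, 56–67%; with (520 − 120)/2 = 200, 60–70%; with 200 + 60 = 260, 69–77%. No single figure can be given.

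**Conclusion.** As written, the Aim 2b repeats cannot answer a question about uptake, because both groupings rest on an event that follows testing. Every non-user leaves the per-protocol set, and 6-month uptake becomes constant or near-constant. Any remaining contrast reflects timing and route of entry. The as-treated repeat is undefined for people who never had a disclosure.

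This is a minor error in a secondary analysis. It affects one outcome in a sensitivity repeat of a moderator analysis. The Aim 1 primary analysis is by intention to treat and stands. The Aim 2a change scores run from baseline to after testing, so they already require a disclosure, and grouping by its method does not fix their value.

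The conclusion assumes that disclosure means Visit 2, as Section 3.3 describes it, and that the repeat covers every model named in its paragraph. It does not depend on the illustrative uptake rates or late shares.

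**What to change.** In the Aim 2b paragraph of Section 4.0, limit the per-protocol and as-treated repeats to outcomes measured after a session (for example knowledge, distress, depression, satisfaction and behaviour), among participants randomised or re-randomised to phone or videoconference. Add that all uptake models, including the moderator models, use randomised groups only, as they stood before the waitlist re-randomisation.

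This takes one or two sentences. It needs no new data and no change to sample size, and it gives up only an analysis that could not have been interpreted.
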